# 2 Schedule of Study Assessments

Procedure	Screening/ Baseline (-28 Days)	Cycle 1 Day 1	Cycle 2 day 28	Every 4 Weeks (1 st 6 cycles)	Maintenance Every 3 months except where Indicated	Addition of Prednisone or Dexamethasone	2 months after the addition of dexamethasone	Off Study 
	ı		ı	1			T	
Informed consent	X	-	-	-	=	-		-
Inclusion/exclusion criteria	X	-	-	-	-	-		-
Complete medical history	X	-	-	-	-	-		-
Confirm diagnosis and stage/type MM	X	-	-	-	-	-		-
Performance status (ECOG)	X	X	-	X		X		X
Concurrent therapy	X	X	-	X		X		X
Safety Assessments: Adverse event query Concomitant Medication query Vital signs/ BSA 12-lead ECG Physical examination CBC w/diff  Serum Chemistry  TSH, T 3 , T 4  Pregnancy testing and counseling  Serum Free Light Chain Serum B12, RBC Folate,  Efficacy measurements: β-2-M Protein electrophoresis (serum and urine) Quantitative immunoglobulins Immunofixation studies (serum and urine)	X X X X X X X X X X 	X X X X X 	X14	X X X X X  X X  X  X -	X 	X X X X X X X X X X X X X		X 12 X X X X X X X X X X X X X X X X X X
Skeletal survey  Dosing: Register patient into RevAssist® program Prescribe study drug¹0 Count study drug returns¹0 Dispense Diary Cards Collect Diary Cards Correlative testing	X -	X  - X	-	X  X  X  X  X		X X X X X		x x x
Bone marrow aspiration for ancillary studies Peripheral blood collection for ancillary studies	Х	$X^{14}$	$X^{14}$ $X^{14}$			X  X 	X 	
Follow-up: Survival					Х			$X^8$

Screening procedures must be done within 28 days of first cycle unless otherwise specified.

Page 9 of 86 Confidential

Starting with Cycle 1, Day 1, and all tests must be done +/- 7 business days of the treatment visit day. However, pregnancy testing must be done strictly as scheduled in footnote #4 below and in sections 6.5.1 and 6.7 without an allowance of +/- 7 days.

\* An unscheduled visit can occur at any time during the study. Source must be maintained for these unscheduled visits. The date for the visit and any data generated must be recorded on the appropriate CRF. Source documents for these unscheduled visits must also be maintained.

<sup>1 All subjects are to have the designated tests performed upon discontinuation of study drug.

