<sup>2 Clinical laboratory examinations include: total protein, albumin, calcium, , glucose, total bilirubin, alkaline phosphatase, AST (SGOT), ALT (SGPT), sodium, potassium, chloride, carbon dioxide, blood urea nitrogen, creatinine, and LDH.

<sup>3 Serum TSH, (Thyroid Stimulating Hormone), T3 and T4 levels every 3 months

<sup>4 Pregnancy testing for females of child bearing potential. A female of childbearing potential (a woman of childbearing potential is a sexually mature woman who: 1) has not undergone a hysterectomy or bilateral oophorectomy or 2) who has not been postmenopausal for at least 24 consecutive months [i.e., who has had menses at any time in the preceding 24 consecutive months]). Pregnancy testing must be performed 10 to 14 days and again within 24 hours prior to prescribing lenalidomide for Cycle 1. (prescriptions must be filled within 7 days). FCBP with regular or no menstruation must have a pregnancy test weekly for the first 4 weeks and then every 28 days while on therapy (including breaks in therapy); at discontinuation of lenalidomide and at Day 28 post the last dose of lenalidomide. Females with irregular menstruation must have a pregnancy test weekly for the first 4 weeks and then every 14 days while on therapy (including breaks in therapy), at discontinuation of lenalidomide and at Day 14 and Day 28 post the last dose of lenalidomide. (see Appendix VIII: Risks of Fetal Exposure, Pregnancy Testing Guidelines and Acceptable Birth Control Methods).

<sup>5 Skeletal survey is to be performed at baseline, upon addition of corticosteroids (prednisone and / or dexamethasone), discontinuation, and when clinically indicated.

Page 10 of 86 Confidential

 Bone marrow biopsy is to be performed at baseline, after 2 cycles of single agent lenalidomide therapy, to confirm CR, at the time of addition of corticosteroids (prednisone and / or dexamethasone), discontinuation, and when clinically indicated.

-  Survival follow-up to be completed every 3 months.

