#### **12.2.** Efficacy evaluation

#### 12.2.1 Primary efficacy analysis

Progression free survival (PFS) is defined as the time from start of lenalidomide monotherapy to the first occurrence of disease progression or death on study from any cause, whichever occurs earlier. All treated patients will be included in efficacy endpoint analysis. Those patients who are treated on this trial but have not had a relevant event at the time of last follow-up will be included in the analyses of these endpoints as censored observations.

Page 66 of 86 Confidential

The primary endpoint is the point estimate of the 12-month PFS rate for the overall response adaptive approach. Number and percentage of patients who survived greater or equal to 365 days without disease progression will be summarized. The 95% confidence interval will be calculated using the exact binominal method. The PFS curves will be estimated by the Kaplan-Meier method. Median and its 95% confidence intervals will be estimated.

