## 12.2.2 Secondary efficacy analysis

Response will be assessed using the Uniform response criteria set forth by the International myeloma working group (IMWG) (See Appendix II). Frequencies and percentages will be used to summarize for all response categories. The response in this trial is defined as complete remission (CR), stringent complete remission (SRC), very good partial remission (VGPR) and partial remission (PR). The response rate for patients treated with single agent lenalidomide, lenalidomide and prednisone and lenalidomide and low dose dexamethasone will be calculated as the percentage of responders, and the 95% confidence interval will be calculated using the exact binominal method. Logistic regression will be used to investigate relationships of the response rates with baseline and other relevant covariates, if appropriate.

Overall survival (OS) is defined as the time from study entry to death of any cause. The OS curves will be estimated by the Kaplan-Meier method. Median and its 95% confidence intervals will be estimated. The effect of baseline and other relevant covariates will be investigated with Cox regression models, when appropriate. Confidence intervals for the survival probabilities at different points will be constructed as needed. The PFS curve for the patients treated with single agent lenalidomide will also Version. 6 date 4/15/2016

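### PFS is censored at an undefined last follow-up, and after study drug stops the only scheduled follow-up is survival contact, so unassessed time can count as progression-free

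*Combined protocol and SAP*

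**What the plan says.** Section 12.2.1 defines the PFS event as the "first occurrence of disease progression or death on study from any cause, whichever occurs earlier". It analyses everyone who was treated: "All treated patients will be included in efficacy endpoint analysis". Its censoring rule is one sentence: patients who "have not had a relevant event at the time of last follow-up will be included in the analyses of these endpoints as censored observations". The date of last follow-up is not defined there or elsewhere.

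Two summaries of PFS follow. For the primary rate, "Number and percentage of patients who survived greater or equal to 365 days without disease progression will be summarized", with an exact binomial interval. For the curve and the median, "The PFS curves will be estimated by the Kaplan-Meier method".

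Section 12.2.2 adds "Overall survival (OS) is defined as the time from study entry to death of any cause" and gives OS no censoring rule of its own.

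In the Section 2 schedule the row on follow-up reads "Follow-up: Survival". Footnote 8, attached to the Off Study column, reads "Survival follow-up to be completed every 3 months". Footnote 1 requires the designated tests at discontinuation of study drug, and no later disease tests are listed for patients who have stopped.

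**The concern.** Section 8.1.7 lets patients stop without progression, for example through refusal, an adverse event, or lenalidomide being discontinued for any reason. Under Appendix II, progression rests on M-protein, free light chain, marrow, bone or plasmacytoma, or calcium findings. A survival contact shows that the patient is alive and cannot exclude progression.

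Take a patient who stops at month 3 without progression and is contacted until month 15. If last follow-up means the last contact, this patient sits in the PFS risk set for 12 months with no disease assessment after the discontinuation tests, and also passes the 365-day mark. Progression in that time is not seen. The error can only run upward, towards the approach under study. It affects the primary endpoint, which Section 6.2 would set against lenalidomide with low-dose dexamethasone.

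**Working it through.** **The plan's own figure.** Section 12.1 assumes 85% with 60 evaluable patients and states a 95% interval of 73.4% to 92.9%. The exact binomial (Clopper-Pearson) interval for 51/60 is 73.4% to 92.9%, so the figure reproduces. The standard error is √(0.85 × 0.15 / 60) = 4.6 points.

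**Inputs for the censoring effect.**
- From Section 12.1: true 12-month PFS S = 0.85.
- Assumed, because the documents give no figure: a share d has a stopping time uniform over months 0 to 12, independent of prognosis; the hazard is constant; no PFS event after stopping is captured; survival contact runs past month 12.

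**Formula.** A patient with a stopping time shows an event only if it comes before that time. The mean chance of being event-free at a uniform stopping time is

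(1 − S) / (−ln S) = 0.15 / 0.1625 = 0.923.

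The estimate when patients are censored at the last survival contact is therefore

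(1 − d) × 0.85 + d × 0.923.

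On this reading nobody leaves the risk set before month 12. The Kaplan-Meier value and the simple 365-day proportion then coincide, so the figures apply to both.

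| d | Censored at last survival contact | Censored at last disease assessment | Upward bias, points |
|---|---|---|---|
| 10% | 0.765 + 0.092 = 85.7% | 85.0% | 0.7 |
| 15% | 0.7225 + 0.138 = 86.1% | 85.0% | 1.1 |
| 20% | 0.680 + 0.185 = 86.5% | 85.0% | 1.5 |
| 30% | 0.595 + 0.277 = 87.2% | 85.0% | 2.2 |

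A simulation of 2,000,000 patients per setting, run for d = 10%, 20% and 30%, agrees to within 0.1 point. It takes the stop date as the last disease assessment.

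**Sensitivity.**
- If 20% of the hidden events still surface as deaths that count, the bias shrinks by about one fifth.
- At a true 12-month PFS of 70%, the simulated estimate is 71.4% at d = 10% and 74.2% at d = 30%, a bias of 1.4 to 4.2 points.

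**If the hazard rises after stopping** (multipliers assumed, with no source in the documents):
- d = 10%, hazard doubled: truth 84.3%; last survival contact 85.7%; last disease assessment 85.0%.
- d = 30%, hazard tripled: truth 81.3%; last survival contact 87.2%; last disease assessment 85.0%. Of the 5.9-point error, the better censoring date removes 2.2 and leaves 3.7.

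**The 365-day count.** Suppose 6 of 51 patients counted as event-free had in fact stopped without progression before month 12. Counting them as progression-free gives 51/60 = 85%. Counting them as failures gives 45/60 = 75% (62.1% to 85.3%). Failing every early stopper has expected value 0.85 × (1 − d), which is 76.5% at d = 10% and 59.5% at d = 30%. That is a much larger distortion in the other direction.

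**The case against.** The best reply is that this is an ambiguity and not a stated wrong rule. The sentence does not say that PFS and OS share a date, and *relevant event* can be read endpoint by endpoint. The documents also use follow-up for disease: footnote 15 follows maintenance patients for progression, and Section 9.7.4.1 names follow-up and survival separately. Limiting deaths to those on study would fit PFS observation that ends when the patient leaves. An analyst could therefore choose the last disease assessment unprompted. This stands as far as it goes: the literal reading is not certain. However, nothing requires the better reading, and the disease follow-up described in footnote 15 and Section 9.7.4.1 is for patients in maintenance, not for those who have stopped.

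It is also fair that the bias is small beside an interval about 19 points wide, that the trial is sized for precision with no hypothesis test, and that the effect largely vanishes if disease assessments in fact continue after stopping. These points limit the size. They do not make a survival contact evidence of being progression-free.

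A reader might infer that the rule overstates PFS by as much as 5 or 6 points. The documents do not support that. Such figures need an assumed two- or threefold hazard after stopping, and most of that error at the upper end is informative censoring, which a better censoring date leaves in place.

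**Conclusion.** The point holds as a gap in the censoring rule that, read literally, biases 12-month PFS upward. The rule itself contributes about 0.7 to 2.2 points at a true 85%. This rests on 10% to 30% stopping uniformly in year 1, a constant hazard and no later events captured. The stopping shares are assumptions. The bias is below one standard error (4.6 points), but it is systematic, so a larger sample would not remove it.

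Two stronger conclusions might be drawn and are not supported. The documents do not establish that the analysis will carry early stoppers as progression-free, only that the text permits it. Nor does the size threaten the contrast in Section 12.1: the assumed 85% and the reference of about 70% lie 15 points apart.

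**What to change.** In Section 12.2.1, replace the censoring sentence with two rules. Patients without progression or death are censored for PFS at the last disease assessment adequate to exclude progression. Patients not known to have died are censored for OS at the last date known alive. Survival contacts then serve OS only.

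Take the 12-month PFS rate and its interval from the Kaplan-Meier estimate under that rule. Keep the 365-day count as a supporting summary that does not treat a patient as progression-free on survival contact alone, and report beside it how many patients lack an assessment at 12 months. Do not turn those patients into failures in the primary estimate.

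The cost is analysis text only, because the schedule already yields the assessment dates. The estimate will be slightly lower and the interval slightly wider. The primary interval is no longer exact binomial, which should be stated openly since accrual has closed. If the hazard rises after stopping, the change removes the false event-free time but not the remaining informative-censoring bias, and the report should say so.

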## **Exploratory**

- 1-Measure a lenalidomide induced tumor specific immune response and correlate the tumor specific immune response with corticosteroid use, response to therapy and duration of response
- 2- To evaluate the impact of lenalidomide mono-therapy on expression of tumor suppression genes and cell cycle regulators

STUDY DURATION: Patients will receive study therapy until evidence of disease progression on lenalidomide and low dose dexamethasone, unacceptable toxicity or withdrawal of consent

**TOTAL SAMPLE SIZE:** approximately 30 patients enrolled at Moffitt and 30 patients enrolled in a parallel identical design study in multiple sites in South Korea.

**STUDY DRUG SUPPLIES:** Lenalidomide capsules will be supplied by Celgene Corporation at no charge through the RevAssist® program.

Commercial supplies of dexamethasone (Decadron®) and prednisone tablets will be utilized.

Commercial supplies of aspirin will be utilized.

Page 7 of 86 Confidential

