#### **DOSING REGIMENS:**

- Oral Lenalidomide (R) will be administered every 28 days as follows:
  - 25 mg QD PO daily on Days 1-21 followed by 7 days rest (10 mg dose will be used for patients with a Creatinine clearance < 60 ml/min)
- Oral Prednisone (100 mg) will be administered on days 1 to 5 of every 28 days cycle in patients receiving combination lenalidomide and prednisone (LP).
- Oral dexamethasone (40 mg) will be administered once a week in patients receiving lenalidomide and low dose dexamethasone (Ld).

All subjects will also receive concomitant aspirin 81 mg PO daily. For patients who cannot tolerate aspirin, low molecular weight heparin or therapeutic doses of coumadin may be used in place of aspirin.

#### Rationale for Amendment 6

MCC16018 has enrolled 30 patients from 2/2010 to 6/2013. It has been closed to accrual since 10/2013 given it met its accrual target. Currently, six patients only continue on treatment, for now 2-4 years. We anticipate to final close the study as soon as a manuscript has been published. Of note, lenalidomide was approved by the FDA for newly diagnosed multiple myeloma patients in 2/2015. MCC16018 involves lenalidomide based therapy for newly diagnosed multiple myeloma and is thus currently considered standard of care (although that use was considered investigational at the time of initiation and completion of accrual of the study). Accordingly, we propose to collect more limited data pertaining to the current treatment of study subject as of 2/2016 until the final closure of the trial. Specifically, we will only plan to capture only serious adverse events (SAE), response and follow up data. Patients will continue on treatment and undergo standard of care monitoring which is at the discretion of the treating physician.

The changes made with this amendment will serve several purposes:

- 1- Decrease the burden on patients to comply with study requirement (for example, comply with study visit timeframe).
- 2- Decrease the number of deviations due to non-compliance with study requirements (such as missed 24h urine protein electrophoresis, laboratory testing outside the window).
- 3- Decrease the burden to the study team which would otherwise continue to collect additional data which will not aid in the overall interpretation of the study results (it is unlikely that a new toxicity to lenalidomide will be encountered in this study population that have been on this treatment for now 2-4 years on average)

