#### **8.1.7.** Discontinuation from treatment

The following events are considered sufficient reasons for discontinuing a subject from study drug:

- Subject declines further study participation.
- Adverse event(s) (AEs) that, in the judgment of the Investigator, may cause severe or permanent harm or which rule out continuation of study drug.

Page 48 of 86 Confidential

- Major violation of the study protocol.
- Progression of disease/unsatisfactory therapeutic effect

Page 49 of 86 Confidential

- Death
- Pregnancy or a positive pregnancy test
- Discontinuation of lenalidomide for any reason
- Subject lost to follow-up
- If for any other reason, must be specified in the data collection system.

Study Closure

Reasons for discontinuation should be recorded in the data collection system and in the subject's medical records.

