## 12.1. Sample size:

The primary endpoint is 12-month PFS for the overall response adaptive approach. Based on the E4A03 and SWOG 2032 studies, the 12-month PFS is approximately 70% for patients treated with lenalidomide low dose dexamethasone. The sample size determination is primarily based on the consideration of providing an estimate of the 12-month PFS with reasonable precision. We estimate the 12-month PFS in the response adapted approach is 85%. With a sample size of 60 evaluable patients (30 from Moffitt and 30 from sites in South Korea), its 95% confidence interval is 73.4-92.9%.

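### Primary 12-month PFS is a raw percentage with an exact binomial interval, so a patient censored before day 365 counts as a failure if Section 12.2.1 is followed as written

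*Combined protocol and SAP*

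**What the plan says.** Section 12.2.1 (Primary efficacy analysis) makes three statements about the same patients.

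- On the analysis set: "All treated patients will be included in efficacy endpoint analysis".
- On patients with no event at last follow-up: they "will be included in the analyses of these endpoints as censored observations".
- On the primary endpoint, which is the point estimate of the 12-month PFS rate: "Number and percentage of patients who survived greater or equal to 365 days without disease progression will be summarized". The 95% interval is exact binomial.

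Kaplan-Meier appears in the same section only for the PFS curves, followed by the median. Section 12.2.2, in its paragraph on overall survival, adds: "Confidence intervals for the survival probabilities at different points will be constructed as needed". Section 12.2.1 has no such sentence for the primary PFS rate.

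Section 12.1 sizes the trial on precision. For an assumed rate of 85% in 60 evaluable patients, "its 95% confidence interval is 73.4-92.9" percent.

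The protocol foresees exits without progression. The Synopsis entry on study duration ends therapy for progression or for "unacceptable toxicity or withdrawal of consent", and Section 8.1.7 lists "Subject lost to follow-up". Section 6.1 replaces patients who stop drug for reasons other than progression, but only if they stop before completing the first cycle.

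**The concern.** A binomial proportion needs a known yes or no at day 365 for every patient in the denominator. Time-to-event data with censoring do not supply that. Take a patient last seen progression-free at day 200. Under the all-treated rule this patient is in the denominator. The patient has not been observed for 365 days without progression, so cannot be in the numerator. Section 12.2.1 calls the same patient censored.

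Three counting rules are possible: failure, exclusion, or event-free. The plan names none of them, and its wording taken as it stands produces the first. The plan also does not say whether progression is still recorded after study drug stops, which decides how many patients are affected. A patient known to be progression-free at day 365 is a success under any rule, so only those whose PFS follow-up ends earlier matter.

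This is the primary figure of a single-arm trial. Section 6.2 says outcomes will be compared with lenalidomide plus low-dose dexamethasone, for which Section 12.1 gives about 70%. A figure that is too low, and that disagrees with the 12-month point on the trial's own PFS curve, could mislead that reading. The same early leaver would be a failure for 12-month PFS and censored for overall survival.

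**Working it through.** **Inputs.** From Section 12.1: n = 60, assumed 12-month PFS 85%, reference about 70%. From Section 12.2.1: all treated patients as denominator, exact 95% interval. The rate of censoring before day 365 is not given and is assumed below.

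**Step 1: the plan's own figure.** 0.85 × 60 = 51. The Clopper-Pearson interval for 51/60 is 73.4-92.9%, which matches Section 12.1. The Wald interval (76.0-94.0%) and the Wilson interval (73.9-91.9%) do not match. The stated precision therefore assumes that day-365 status is known in all 60 patients.

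**Step 2: a small case.** Keep 9 events and let 2 of the 51 others be censored before day 365, with event and censoring times spread evenly over the year.

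- Count as written: 49/60 = 81.7%, exact interval 69.6-90.5%. Each early censoring costs 1/60 = 1.67 points.
- Kaplan-Meier: the numbers at risk at the nine events are 60, 59, 57, 56, 55, 54, 53, 51 and 50. The product of (1 − 1/risk) is (58/60) × (52/57) × (49/51) = 0.847. With Greenwood variance on the log-log scale the interval is 72.7-91.7%.

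**Step 3: a range of dropout.** Let c be the assumed 12-month probability of independent dropout, with constant hazards λ = −ln 0.85 for events and μ = −ln(1 − c) for dropout.

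- Failure rule: expected rate S = exp(−(λ+μ)) = 0.85 × (1 − c).
- Event fraction: E = λ/(λ+μ) × (1 − exp(−(λ+μ))).
- Exclusion rule: approximately S/(S+E).
- Event-free rule: 1 − E.

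Coverage of the true 85% by each 95% interval was simulated with n = 60 and 20,000 runs.

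| Assumed dropout | Failure rule: expected (coverage) | Exclusion: expected (coverage) | Event-free: expected (coverage) | Kaplan-Meier coverage |
|---|---|---|---|---|
| 5% | 80.8% (about 90%) | 84.7% (96%) | 85.4% (97%) | about 96% |
| 10% | 76.5% (about 67%) | 84.3% (97%) | 85.7% (97%) | about 96% |
| 20% | 68.0% (about 15%) | 83.5% (96%) | 86.5% (96%) | about 96% |

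**Step 4: dependent dropout.** Assume 10% leave and their event hazard then triples. The true 12-month PFS becomes 83.7%. Kaplan-Meier still targets 85.0%, which is 1.3 points too high. The failure count expects 76.5%, which is 7.2 points too low.

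**Step 5: no early censoring.** Both methods give 85.0% and there is no bias.

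**The case against.** The strongest reply is that the damage belongs to one of three readings. If early-censored patients are excluded or counted as event-free, the exact interval keeps about 96-97% coverage and the bias is at most 1.5 points. Section 12.1 speaks of evaluable patients and Section 6.1 replaces early leavers, which could point towards exclusion. That reading does not hold against the text. Section 6.1 covers only the first cycle, and Section 12.2.1 says all treated patients are included. It is true, however, that the binomial method is not at fault in itself. The fault lies in combining it with an all-treated denominator and no rule for censoring.

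A second reply is that the proportion known to be progression-free at one year is a legitimate, conservative phase 2 summary, and that the Kaplan-Meier curve will stand beside it. That would be fair if the plan said so. It calls these patients censored instead.

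Three further points stand. The dropout rates are assumed. The 70% reference is not a formal success threshold, so a lower limit falling below it triggers no decision. In the copy reviewed, the Section 12.2.2 paragraph breaks off mid-sentence where it turns to PFS on single-agent lenalidomide, so the contrast with overall survival is supporting evidence only.

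The most serious objection is timing. The trial is open-label and "MCC16018 has enrolled 30 patients from 2/2010 to 6/2013", while this version is dated 4/2016, so every Moffitt patient is past 365 days from enrolment. Kaplan-Meier can never fall below the literal count, so the switch can only favour the treatment. This is why both figures must be reported.

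**Conclusion.** The concern holds. Section 12.2.1, followed as written, counts a patient censored before day 365 as a failure in the primary endpoint while describing that patient as censored. The bias is downward, at 1.67 points per such patient when n is 60. Under a true rate of 85% and assumed independent dropout of 5% to 20%, the expected rate falls by 4.2 to 17 points and interval coverage drops from about 90% to about 15%.

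These sizes depend wholly on how many patients leave PFS follow-up within the first year, which the documents do not state. At Moffitt the data cut-off adds no early censoring, so only true early leavers count there. If there were none at any site, nothing changes. The stated interval of 73.4-92.9% is arithmetically right, but it assumes complete day-365 status. The plan should be corrected, because the primary figure should not rest on a counting rule that is implied and not stated.

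**What to change.** In Section 12.2.1:

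- Name the Kaplan-Meier PFS probability at day 365, with a 95% interval from Greenwood variance on the log-log scale, as the primary 12-month estimate in all treated patients.
- State that replaced patients who took lenalidomide are included.
- Report the exact binomial proportion beside it, with patients censored before day 365 counted as failures, as a conservative sensitivity analysis. Exits for toxicity may not be independent of progression, so this bound is informative.
- Give the number of patients censored before day 365, by reason.

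In Section 12.1, label 73.4-92.9% as the precision expected with no early censoring.

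The cost is wording only, with no new data or visits. The Kaplan-Meier interval is approximate where the binomial one is exact, and the estimate is unbiased only under independent censoring. Because the change comes late and can only raise the estimate, it should be dated, documented as made after Moffitt accrual was complete, and presented with both figures.
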